## 5.7. **Post-Prostatectomy Procedures**

- 5.7.1. **PSMA-positive with negative pathology.** Subjects with  $^{68}\text{Ga}$  PSMA-HBED-CC positive nodes without positive nodes on pathology, may be rescanned with CT (or MRI) to determine if the suspicious node was thought to be removed. Additionally, clinicians will have the option to order a 2nd  $^{68}\text{Ga}$  PSMA-HBED-CC PET/CT as described in Section 6.4.4.
- 5.7.2. **PSMA-positive osseous or metastatic lesions.**  $^{68}\text{Ga}$  PSMA-HBED-CC positive osseous or distant metastatic lesions will be followed by other imaging (bone scan, NaF PET, CT or MRI) at the treating physician's discretion and local standard of care.
- 5.7.3. **Biopsy.** Biopsies to determine metastases or provide information for re-staging should be performed at treating physician's discretion and per local

standard of care.

- 5.7.4. **CT or MRI.** Subjects should undergo routine standard of care imaging.
- 5.7.5. Positive disease identified by either Ga PSMA-HBED-CC PET/CT or follow-up conventional imaging will trigger locally performed anatomic measurement of lesion size(s) on both the baseline CT or MRI, and the follow-up CT or MRI of suspected site of disease.

#### 5.8. **General Concomitant Medication and Supportive Care Guidelines**

In general, subjects may receive full concomitant and supportive care throughout this trial with the following considerations:

- Subjects may not receive any other approved or investigational anti-neoplastic therapies for the treatment of prostate cancer from time of consent through prostatectomy.

#### 5.9. **Follow-Up**

- 5.9.1. **Active follow-up.** Subjects will be actively followed for acute adverse events for 10 radioactive half-lives rounded up to the calendar day (as per the established standard). Since Gallium-68 has a half-life of 67.71 minutes the active follow-up will be a minimum of 1 calendar day.

- 5.9.2. **Long term follow-up.** After the active follow-up period, the subject will return to standard follow-up with their physician. Subject's outcome should be followed through passive chart review. Data collected must minimally include subsequent PSA measurements, and any evidence of disease progression. Contact with subject and/or subject's treating physicians may occur to better define treatment outcomes.

#### 5.10. **Criteria for removal from study**

- **Consent.** Subjects must be able to continue to provide consent for this study. If a treating physician or study team member believes a subject can no longer provide prospective consent, the investigator will be contacted to determine if the subject can provide consent and is able to continue on study.
- **Refusal to continue treatment.** In this event, the reasons for withdrawal will be documented.

### 6. PATIENT ASSESSMENTS

#### 6.1. **Post-consent Baseline Data Collection**

Post-consent, the following data should be collected

- 6.1.1. **Pathology.** A copy of the pathology report documenting the Gleason score should be obtained. Also, obtain a copy of any pathology reports 3 months prior to the Ga PSMA-HBED-CC PET/CT.
- 6.1.2. **Bone scan.** If a bone scan was performed within 3 months of Ga PSMA-HBED-CC PET/CT, obtain a copy of the images and the report.
- 6.1.3. **MRI.** If an MRI was performed within 3 months of Ga PSMA-HBED-CC PET/CT, obtain a copy of the images and the report.
- 6.1.4. **CT scan.** If a CT was performed within 3 months of Ga PSMA-HBED-CC

PET/CT, obtain a copy of the images and the report.

6.1.5. **PSA.** Baseline PSA lab tests within 3 months of Ga PSMA-HBED-CC PET/CT should be obtained.

## 6.2. **Pre-Imaging Assessments (Baselines)**

6.2.1. **Constitutional adverse events.** A baseline evaluation will be obtained prior to injection and graded according to NCI's Common Toxicity Criteria (CTCAE v4).

6.2.2. **Vital signs.** Heart rate, blood pressure, and temperature will be obtained immediately before and after injection of Ga PSMA-HBED-CC, in a supine position.

## 6.3. **Post-Imaging Assessments**

6.3.1. **Vital signs.** Heart rate, blood pressure, and temperature will be obtained when subject is supine immediately after the imaging session.

6.3.2. **Constitutional adverse events.** Prior to discharge from the PET Imaging Center the subject will be assessed for untoward medical event(s) that have occurred since injection of Ga PSMA-HBED-CC. These will be graded with CTCAE.

6.3.3. **Symptom review.** Subject will be contacted by telephone or in person between 1 to 3 business days after PSMA-HBED-CC imaging to screen for adverse events. Subject must be contacted at least once after 24 hours post-injection.

## 6.4. **Follow-up**

6.4.1. **Pathology.** Results from pathology ordered per standard of care up to 12 months post Ga PSMA-HBED-CC PET/CT, will be obtained for study analysis.

6.4.2. **Follow-up imaging.** Conventional imaging ordered per standard of care up to 12 months post Ga PSMA-HBED-CC PET/CT, will be obtained for study analysis. If the 1st Ga-68 PSMA-HBED-CC PET/CT scan shows lesions outside the pelvic region AND if imaging is NOT obtained per standard of care the research study will obtain a CT (abdomen and pelvis w/ contrast if contrast not contraindicated). Readers will be unblinded to all results and will be specifically informed of the location of the Ga PSMA-HBED-CC PET positive lesions so follow-up measurements may be performed on the same lesions.

6.4.3. **Laboratory.** Results from laboratory reports related to prostate cancer monitoring (e.g. PSA levels) ordered per standard of care up to 12 months post Ga PSMA-HBED-CC PET/CT, will be obtained for study analysis.

6.4.4. **Second Ga PSMA-HBED-CC PET/CT (if medically indicated).** If the 1st Ga PSMA-HBED-CC PET/CT scan shows lymph nodes or visceral (soft tissue) lesions positive for prostate cancer disease, but surgery or biopsy results in negative pathology; the subject may be asked to return to complete a 2nd Ga-68 PSMA-HBED-CC PET/CT imaging visit.

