#### 5.1. Imaging preparation

- 5.1.1. **Oral hydration.** Participants will be encouraged to maximize hydration the day before and day of  $^{68}\text{Ga}$  PSMA-HBED-CC imaging.
- 5.1.2. **Furosemide.** 20 mg furosemide (IV push) will be administered concurrently or immediately after radiotracer administration to minimize PET scatter artifacts from excreted radiotracer accumulation in the kidney and urinary

bladder.

- 5.1.3. **Contrast.** Imaging contrast will not be ordered as part of this study.
- 5.1.4. **Voiding.** Participants will be asked to void their bladder immediately prior to radiotracer injection and before imaging.

5.2. **Ga PSMA-HBED-CC administration**

- 5.2.1. **Dose.** 3-7 mCi (111 – 259 MBq). Target 5 mCi.
- 5.2.2. **Route of administration.** Intravenous.
- 5.2.3. **Frequency.** Once per PET scan.
- 5.2.4. **Uptake time.** 75 minutes ± 25 minutes. Target 75 minutes

5.3. **Prohibited Medications**

None.

5.4. **PET/CT Imaging Procedures**

- 5.4.1. **Scan coverage.** Scan coverage will extend from mid-thigh to the base of the skull, starting from the mid-thighs to prevent urinary bladder radiotracer accumulation at the start of PET imaging. Subject to void immediately prior to imaging.
- 5.4.2. **Bed position.** Scan time will be dependent on scanner capabilities. At a minimum, 3 minutes per bed position will be used.
- 5.4.3. **Discharge.** Subject must be monitored for adverse events for a minimum of 2 hours post-injection.
- 5.4.4. **Local Analysis.** A board-certified nuclear medicine physician on-site will interpret the images within 3 business days of the imaging study. These interpretations will not be used for final evaluation, however regional positivity results will be collected as study data.
- 5.4.5. **Internal Blinded Reads.** Imaging data will be interpreted by two different readers in a random order at separate reading sessions. Cross sectional imaging from the PET will be available for anatomic correlation. Final reads for each subject will be interpreted as positive or negative for the presence of pelvic nodal disease, and positive or negative for the presence of osseous metastatic disease and soft tissue metastases outside of the pelvis. All readers will have undergone Ga PSMA PET training.
- 5.4.6. **Results dissemination.** Results will be shared with the subject's urologist and will be included in the subject's medical record.

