## 12. EFFICACY ASSESSMENTS

Determination of efficacy requires two primary assessments.

The first assessment is the clinical read of the  $^{68}\text{Ga}$ -PSMA-HBED-CC PET/CT scan. Trained readers will identify lesions positive for prostate cancer disease, and based on these results, will categorize specifically defined anatomical regions of the subject (Table 12.2) as positive for disease by  $^{68}\text{Ga}$ -PSMA-HBED-CC PET/CT. Criteria are described in Section 12.1 below.

The second assessment is the reference standard determination of disease positivity or negativity also performed on the same specifically defined anatomical regions (Table 12.2). The reference standard definitions are described below, and consist of a combination of pathological confirmation, conventional imaging follow-up evidence, and serial PSA measurements. Criteria are described in Section 12.2 below.

For purposes of endpoints, four major regions are identified for final analysis as defined in Table 12.1. Each region is divided into subregions as defined in Table 12.2. All primary data from  $^{68}\text{Ga}$ -PSMA-HBED-CC PET interpretations, pathology results, and conventional imaging results, will be collected per the subregions defined below. The final region assignments and results will be derived from the subregion data as applicable.

Region	Description
1	Prostate Bed
2	Pelvis outside of prostate bed including lymph nodes
3	Extrapelvic soft tissue, lymph nodes and organ metastases (non-bone)
4	Bone metastases

Table 12-1. Major Analysis Regions

Region 2: Pelvis outside of prostate bed	Region 3: Extrapelvic soft tissue	Region 4: Bone metastases
Right obturator	Lung	Spine
Left obturator	Liver	Ribs
Right external iliac	Pancreas	Pelvis
Left external iliac	Spleen	Extremities
Right internal iliac	Intestine	Skull
Left internal iliac	Mesentary	Sternum
Other pelvic regions	Brain	Clavicle
	Other soft tissue	Other bone
	Abdominal nodes	
	Thoracic nodes	
	Other nodes	

Table 12-2. Subregion Classification

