12.1.1.3. Bone lesions will be considered positive if the  $^{68}\text{Ga}$ -PSMA-

HBED-CC uptake is focal and greater than physiologic bone marrow.

- Bone lesions will be classified by further by region: spine, ribs, pelvis, extremities, skull, sternum, and clavicle, as Defined in Table 12.2. These sub-regions will be correlated with reference standard results in these sub-regions, however this sub-region data will not be directly used for evaluation of the primary or secondary endpoints, but for exploratory analysis.

12.1.1.4. Prostate bed and prostate lesions will be considered positive if the Ga-PSMA-HBED-CC uptake is focal and greater than physiologic background activity of the involvement organ or anatomic site.

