12.2.1.3. Bone lesions: Given the high rate of false negative biopsies for osseous metastases in subjects with prostate cancer, subjects with negative bone biopsies of  $^{68}\text{Ga}$ -PSMA-HBED-CC PET positive lesions will be further evaluated:

- If pathology demonstrates an alternative diagnoses that is known to be  $^{68}\text{Ga}$ -PSMA-HBED-CC positive (eg Renal Cell Carcinoma metastases, Paget's disease), then this will be considered negative for disease.
- If pathology is indeterminate, then follow-up imaging as described below will be performed as per clinical standards at the site.

12.2.1.4. Although not routinely performed during standard practice, immunohistochemical staining for PSMA of tumor specimens (primary and lymph node metastases) may be performed, although not required.

12.2.1.5. All regions not sampled for biopsy/histopathology will be designated as indeterminate for disease by pathology. Conventional imaging follow-up may be used in these cases to determine tissue status.

12.2.2. Follow-up Imaging will be used as a secondary assessment for prostate cancer in the event pathology information is not available:

All subjects will be tracked for follow-up conventional imaging between 3-12 months post  $^{68}\text{Ga}$ -PSMA-HBED-CC (dedicated CT, MRI and/or bone scan) as per site standard of care. If no follow-up imaging has been performed within the 9 months following the  $^{68}\text{Ga}$ -PSMA-HBED-CC scan, then the research study will pay for an additional follow-up CT scan to be performed in the 9-12

month window post-Ga-PSMA-HBED-CC scan. Follow up imaging will only be performed on subjects that have positive Ga-PSMA-HBED-CC findings because conventional imaging assessment for disease is primarily targeting suspicious lesions identified by Ga-PSMA-HBED-CC PET/CT. Interpretation of follow-up imaging will be performed by local read. Preferably, the follow-up conventional imaging should be the same modality/modalities as the initial staging work-up to allow for reproducible and accurate comparisons. Conventional imaging standards as described below will be used to determine tissue positive for prostate cancer disease. Conventional imaging will not be used to determine negative prostate cancer disease regions due to its inherently low negative predictive value.

Tissue positive for prostate cancer disease based on follow-up imaging:

12.2.2.1. Lymph nodes will be assessed by change in size.

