13.3.2. True negative region

13.3.2.1.  **$^{68}\text{Ga}$  PSMA-HBED-CC PET negative for extra-pelvic node metastases by internal blind reader** – and pathology (if available) negative for disease, and, extra-pelvic node not positive for disease by imaging.

13.3.2.2.  **$^{68}\text{Ga}$  PSMA-HBED-CC PET negative for visceral metastases by internal blind reader** – and pathology (if available) negative for disease, and, visceral lesion not positive for disease by imaging.

13.3.2.3.  **$^{68}\text{Ga}$  PSMA-HBED-CC PET negative for osseous metastases by internal blind reader** - and pathology (if available) negative for disease, and, osseous lesion not positive for disease by imaging.

13.3.3. False positive region:

13.3.3.1.  **$^{68}\text{Ga}$  PSMA-HBED-CC PET positive for extra-pelvic nodes by internal blind reader**, pathology (if available) is negative, and imaging after prostatectomy demonstrates that node is not positive for disease.

13.3.3.1.1.  **$^{68}\text{Ga}$  PSMA-HBED-CC PET positive for regional node by internal blind reader**, but pathology (if available) is positive for node but in a different nodal region than the node seen on PSMA PET.

13.3.3.2. **PSMA-HBED-CC PET positive for visceral lesion by internal blind reader**, pathology (if available) is negative, and imaging after prostatectomy demonstrates that the visceral lesion is not positive for disease.

13.3.3.2.1.  **$^{68}\text{Ga}$  PSMA-HBED-CC PET positive for visceral lesion by internal blind reader**, but pathology (if available) is positive for visceral lesion but in a different region than the visceral region seen on PSMA PET.

13.3.3.3.  **$^{68}\text{Ga}$  PSMA-HBED-CC PET positive for osseous lesion by internal blind reader**, pathology (if available) is negative, and imaging after prostatectomy demonstrates that the osseous lesion is not positive for disease

13.3.3.3.1.  **$^{68}\text{Ga}$  PSMA-HBED-CC PET positive for osseous lesion by internal blind reader**, but pathology (if available) is positive for osseous lesion but in a different region than the osseous region seen on PSMA PET.

13.3.4. False negative region:

13.3.4.1.  **$^{68}\text{Ga}$  PSMA-HBED-CC PET negative for extra-pelvic nodes**

by internal blind reader, and pathology (if available) positive for that node, or, extra-pelvic node positive for disease by imaging as defined in Section 12.2.2.1.

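### The research follow-up CT in 6.4.2 is prompted by any PET lesion outside the pelvis but covers only abdomen and pelvis, so it cannot assess some of the lesions it is meant to verify

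*Combined protocol and SAP*

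**What the plan says.** Section 6.4.2 orders a research CT if the first PET/CT "shows lesions outside the pelvic region AND if imaging is NOT obtained per standard of care". It then fixes the field: "the research study will obtain a CT (abdomen and pelvis w/ contrast if contrast not contraindicated"). The next sentence gives the purpose. Readers are told where the PET-positive lesions are so that "follow-up measurements may be performed on the same lesions".

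The scan that creates the trigger sees more of the body. Section 5.4.1 states: "Scan coverage will extend from mid-thigh to the base of the skull". Table 12-1 defines Region 3 as "Extrapelvic soft tissue, lymph nodes and organ metastases (non-bone"), and Table 12-2 lists lung, thoracic nodes and other nodes within it. For Region 4, section 12.1.1.3 names "spine, ribs, pelvis, extremities, skull, sternum, and clavicle".

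Section 12.2.2 describes a study-paid scan a second time. If there has been no follow-up imaging in the 9 months after the PET, "then the research study will pay for an additional follow-up CT scan to be performed in the 9-12" month window. That section limits follow-up imaging to PET-positive subjects and explains that its main target is the suspicious PET lesions. It states no body coverage.

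**The concern.** The trigger, the field and the purpose of one scan do not fit together. A man whose only extra-pelvic finding is a mediastinal or neck node meets the trigger. He then has a contrast CT that does not include the node, and the planned measurement cannot be made.

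This matters for the secondary endpoints: accuracy for extra-pelvic nodal, visceral and osseous metastases. When there is no biopsy and no standard imaging, this CT is the planned source of verification. If it works below the diaphragm and not above it, whether a PET-positive region can be verified depends on where the lesion lies, and the reported figures describe a selected set of sites.

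**Working it through.** No arithmetic in the plan bears on this point, so the check sets the sections side by side.

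**Step 1: can an out-of-field lesion set off the scan?** The trigger is any lesion outside the pelvis (6.4.2). The PET covers mid-thigh to skull base (5.4.1), which includes chest and neck. Table 12-2 gives those sites their own entries. So yes.

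**Step 2: does another section supply the missing coverage?** Section 12.2.2 gives no field, so it neither repeats nor widens the abdomen-and-pelvis limit. Section 5.7.2 has osseous and distant PET-positive lesions followed by other imaging, but at the treating physician's discretion. No section adds a chest, neck or lesion-directed research scan.

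**Step 3: what does the reference standard need when there is no pathology?**

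| Lesion type | Routes to a positive reference result | Is a follow-up image of the site needed? |
|---|---|---|
| Lymph node (12.2.2.1) | Size change, with or without a PSA change, according to treatment; or a PSA fall above 50% after targeted treatment alone, with no enlargement | Yes, on every route |
| Visceral (12.2.2.2) | Size change, with or without a PSA change; or a PSA fall above 50% after targeted treatment alone | Yes, except on the PSA-only route |
| Bone (12.2.2.3) | Baseline sclerosis on the CT portion of the PET or a CT within 30 days; baseline bone scan or MRI within one month; new lesion within 12 months; or a PSA fall above 50% after targeted treatment alone | Not for the baseline and PSA routes |

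The clearest cases are therefore thoracic and neck nodes and most lung lesions. Next come sternum or clavicle lesions with no correlate on baseline CT, bone scan or MRI. An abdominal CT usually includes the lung bases and lowest ribs, so chest and rib lesions are not all affected.

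**Step 4: how is such a region classified?** With no pathology and no criterion met, 12.2.2 makes it indeterminate. Section 13.3.5.1 makes a region with insufficient data non-evaluable.

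**Step 5: what does the loss do to the estimates?** Let k truly diseased, PET-positive regions become non-evaluable, out of TP true positives, with FP false positives and FN false negatives.

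- Sensitivity in its usual sense goes from TP/(TP + FN) to (TP − k)/(TP − k + FN). This is lower whenever FN > 0.
- PPV goes from TP/(TP + FP) to (TP − k)/(TP − k + FP). If FP = 0 and k < TP, it stays at 1 and only precision is lost.

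If the lost regions are not diseased, potential false positives disappear instead and PPV moves the other way. The documents do not allow the direction of the net effect to be fixed.

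**The case against.** The strongest reply is that the gap is narrow. The CT is a fallback for men without standard imaging. Biopsy remains possible, bone lesions have baseline routes, and visceral and bone lesions treated with targeted therapy alone can qualify on PSA. The secondary endpoints are descriptive, without significance testing, in a planned 30 patients. All of this stands, and it limits how often the problem can arise. It does not make the scan able to assess a lesion outside its field.

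Two stronger readings are tempting, and the documents do not support them.

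- A reader might infer that an unseen lesion would be scored a false positive and so lower PPV. For bone, section 13.3.3.3 requires that "imaging after prostatectomy demonstrates that the osseous lesion is not positive for disease", and the nodal and visceral rules are parallel. A CT that omits the lesion demonstrates nothing about it. Section 12.2.2 also says that conventional imaging is not used to establish negative regions. The non-evaluable result is the natural one. Some tension remains between the false-positive rules and that statement in 12.2.2, but it would exist for a lesion inside the field too and is a separate matter.
- A reader might infer the size of the problem by counting how many of the 19 sub-regions in Table 12-2 (11 in Region 3, 8 in Region 4) lie outside the abdomen and pelvis. That count does not measure it. The PET stops at the skull base, so brain and skull-vault lesions would rarely be the trigger, and ribs are partly covered. Sections 12.1.1.1 to 12.1.1.3 also say that sub-region data are not used directly for the primary or secondary endpoints.

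**Conclusion.** The mismatch is real, and no other section removes it. Followed exactly, 6.4.2 can give a man a research CT that cannot assess the lesion that prompted it. The consequence is loss of PET-positive regions from the secondary endpoints by anatomical site, through the indeterminate and non-evaluable categories.

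The size cannot be computed. A region is affected only if all of these hold: it contains a PET-positive lesion above the abdomen; there is no pathology; there is no standard imaging; no baseline bone or PSA-only route applies; and no other lesion in the same region has been confirmed. The documents give none of these frequencies. The number may be zero and is probably small. With few extra-pelvic positives likely in 30 patients, however, each lost region would carry weight.

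The primary pelvic nodal endpoint is not directly affected. This is an inexpensive improvement to the verification of the secondary endpoints, not a flaw in the main analysis. It assumes that abdomen and pelvis in 6.4.2 is meant as the full field and not as an example.

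**What to change.** Reconcile 6.4.2 with 12.2.2 so that both describe the same research CT, with one trigger, one time window and one statement of field. State the field by purpose: it includes every PET-positive extra-pelvic site that the scan is meant to verify.

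Optionally, confirm in 13.3.3 that imaging which omits the PET-positive site cannot count as demonstrating absence of disease there. Report the number of regions that are non-evaluable for this reason, by lesion type, next to the secondary estimates.

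The cost is a protocol wording change and, in the few men concerned, a longer CT field in the same session, with some added radiation and expense. The classification sentence and the extra count cost nothing beyond the text.
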